**Table 9.3: Probability that the trial will be terminated early due to excessive toxicity on arm A**

True proportion of the toxicity	0.10	0.15	0.20	0.25	0.30	0.35
Probability of early termination	0.026	0.15	0.39	0.65	0.84	0.94

### 9.3 Statistical Consideration for Objective Response, Toxicity and Time to Treatment Deterioration

#### 9.3.1 Objective response

Objective response in the two arms will be evaluated by comparing objective response rate (ORR, PR+CR) using a Fisher's exact test on the intention-to-treat patients with one-sided type I error of 2.5%. The primary analysis of ORR will be evaluated on the first 360 patients enrolled for the PFS analysis, a secondary analysis of ORR will be conducted on all patients. Patients who are unevaluable for response and patients never starting protocol therapy will be included as non-responders in this analysis. Based on the BOLERO-2 results, the ORR will be about 0.4% on arm B. For the primary analysis of objective response, with 180 refractory patients on each arm, the study will have 86% power to detect an increase to a 6% objective response rate on arm A.

#### 9.3.2 Toxicity

Another secondary endpoint of the study is to evaluate toxicities. Toxicity will be evaluated on the first 360 patients for the PFS analysis and on all patients for the OS analysis. All patients who start protocol therapy (i.e., receive at least one dose of protocol treatment) will be included in toxicity analysis. For the 360 patients for the PFS analysis, assuming 9 patients (9/180=5%) will not start protocol therapy in each arm, with 171 evaluable patients per arm, there is 92% power to detect a difference in grades 3-4 toxicity rate of 24% vs. 10% between arms A and B, assuming an one-sided type I error rate of 2.5%, based on the Fisher's exact test. For each arm, with 171 patients, the binomial exact 95% confidence interval for toxicity rate would be no wider than 0.16.

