PRO assessments at treatment discontinuation and 4 weeks post-treatment discontinuation for all participants regardless of the reason for treatment discontinuation (toxicity, progression) will provide valuable information on HRQL and symptom burden. As noted by Rini et al. HRQL can appear to improve overall as the trial progresses due to participant selection bias. Participants with poorer performance status, more aggressive disease, and greater treatment toxicities come off treatment earlier. We may observe a high rate of attrition due to progression of illness. Patients on EE are expected to remain on treatment longer than patients on EP due to anticipated benefit in PFS. To obtain an unbiased assessment of HRQL and treatment toxicities, PRO assessment at the end of treatment and a short period of time following end of treatment (4 weeks) for all participants is needed. Otherwise, PRO assessments only capture data on participants who remain on treatment and are likely to be healthier, therefore, presenting a biased source of data that will likely indicate that HRQL improves over time. In addition, the assessment 4 weeks post-end of treatment will evaluate whether entinostat-related symptoms resolve within 4 weeks. This design (retaining participants who discontinue treatment) has been employed with other PROs studies such as the side effect sub-study of MA.27.

Rev. Add7

A PRO measure of breast cancer-specific symptoms will be administered at baseline, and every 28-day cycle for the first six months after randomization, and then every two cycles between 6 months and 1 year. After 1 year, the FBSI will be administered on the same schedule as tumor assessments until disease progression. The FBSI will be administered more frequently to allow for an assessment of time to treatment deterioration (TTD), a critical secondary endpoint.

The PRO measure of adherence to therapy, the Medication Adherence Scale - , will be administered as outlined in Section [5.6.3](#) (before Cycle 4, 7, 13, and end of protocol therapy). With the exception of baseline, these assessment time points correspond with other study PRO.

The FBSI and Medication Adherence Scale include 8 and 8 items each and the anticipated time to complete the 16 items is roughly 5-6 minutes. Please note there will be one Medication Adherence Scale form completed for each agent (entinostat/placebo and exemestane).

Rev. Add7

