### 9.2 Study Design

Patients with histologic confirmation of invasive adenocarcinoma of the breast will be randomized according to the permuted block algorithm with a 1:1 randomization ratio to arms A and B. Stratification factors include:

- Setting in which patient developed resistance to prior non steroidal AI treatment (adjuvant vs. metastatic)
- Geographic region (USA vs. other)
- Visceral disease (yes vs. no)
- Prior fulvestrant use (yes vs. no)

**NOTE:** Visceral disease is defined as lung and/or liver involvement.

Taking into consideration the accrual rates of the BOLERO-2 study (40 patients/month, 700 patients over 18 months with 24 international sites), the ENCORE 301 study (5 patients/month, 130 patients over 2 years at 38 sites US and international) and the CONFIRM study (24 patients/month at 128 sites), all of which have been conducted in the AI refractory setting, and the 1st line SWOG

S0226 study (10 patients/month, 700 patients over 6 years), we anticipate an accrual rate of approximately 15 patients per month in our study.

Enrollment of 600 patients will be required to provide adequate power for the OS endpoint (see Section [9.2.2](#)). The first 360 patients will be used for the primary evaluation of PFS (see Section [9.2.1](#)), objective response rate (ORR), toxicity, time to treatment deterioration and patient-reported outcomes. If the PFS analysis is positive, the data for first 360 patients would be used for a submission to the FDA. At the time of final analysis for the OS endpoint, secondary analyses of PFS, objective response and toxicity will be conducted in all 600 patients, along with the primary analyses for the pharmacodynamic acetylation marker data and adherence to protocol therapy data. Imaging studies for all 600 participants will be collected and archived at the ACR Imaging Core Laboratory.

For purposes of comparability to the phase 3 study of exemestane in advanced breast cancer patients by Chia et al., enrollment in this study will attempt to achieve a target patient population that consists of approximately 80% of patients having measurable disease (with at least 1 measurable lesion at baseline assessment and identification of up to 5 total target lesions [maximum of 2 lesions per organ] and 5 total non-target lesions) and approximately 20% of patients having non-measurable disease only.

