at diagnosis, prior adjuvant chemotherapy, prior hormonal therapy, et al. The assumption of proportionality in the Cox models will be assessed by investigating the weighted Schoenfeld residuals for each predictor. Patients with missing values for covariates will be excluded from modeling when the proportion of missingness is less than 5% and will be imputed appropriately if the proportion of missingness is  $\geq 5\%$ . ORR will be summarized along with the exact binomial 95% confidence interval and compared between the two arms using Fisher's exact tests.

TTD is defined as time from randomization to disease progression or death or worsening of symptoms, whichever occurs first. All primary analysis for TTD will be based on all cases receiving at least one dose of protocol treatment (i.e., all treated population). The distribution of TTD will be estimated using Kaplan-Meier method, and TTD comparisons between treatment arms will be tested primarily using log-rank test. Cox proportional-hazards models will be conducted to estimate the HR for treatment effect for TTD as a supportive analysis. Same factors included in the multivariable Cox model for PFS and baseline symptom level will be included as predictors for TTD.

Analyses pertaining to toxicity will be based on all treated cases. Adverse events will be graded using the National Cancer Institute (NCI) Common Terminology Criteria for Adverse Events (CTCAE). All treatment-emergent and baseline adverse events and hematological/biochemical toxicities based on laboratory measurements, as well as drug related AE's, will be summarized by treatment group and NCI CTCAE worst grade. The incidence of deaths and treatment-emergent serious adverse events (defined as number of patients experiencing the AE divided by all treated patients) will be summarized and compared between treatment arms using Fisher's exact test. Also, the incidence of adverse events leading to discontinuation of investigational product and/or withdrawal from the study will be summarized and listed.

In all analyses, P-values will be two-sided. A level of 0.2% will be considered statistically significant for stratified log rank test for the primary PFS analysis. For OS comparison, the significance level for stratified log rank test will be 4.8%. For all other tests, a level of 5% will be considered statistically significant.

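### Clinician-graded toxicity is compared between arms only by crude whole-period incidence, which cannot separate a higher toxicity risk from the longer treatment expected on arm A

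*Combined protocol and SAP*

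**What the plan says.** **Grade 3-4 toxicity.** Section 9.3.2 includes everyone who received at least one dose. It makes the calculation "assuming 9 patients (9/180=5%) will not start protocol therapy in each arm, with 171 evaluable patients per arm" and states that "there is 92% power to detect a difference in grades 3-4 toxicity rate of 24% vs. 10% between arms A and B", one-sided at 2.5%, "based on the Fisher's exact test". The evaluation is made on the first 360 patients and again on all patients at the OS analysis.

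**Deaths and serious adverse events.** Section 9.4 has the incidence of deaths and treatment-emergent SAEs "defined as number of patients experiencing the AE divided by all treated patients) will be summarized and compared between treatment arms", again with Fisher's exact test. Other adverse events are tabulated by arm and worst grade. P-values are two-sided, and "For all other tests, a level of 5% will be considered statistically significant".

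**Time on treatment.** Under Section 5.1.1, cycles repeat until progression or unacceptable toxicity. Section 9.2.1 assumes median PFS of 4.1 months on arm B and 7.1 months on arm A. Section 5.6.3 says: "Patients on EE are expected to remain on treatment longer than patients on EP due to anticipated benefit in PFS" (EE is arm A, EP is arm B).

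**Patient-reported outcomes.** Section 9.6 fixes the primary comparison of quality of life and of four entinostat-associated symptoms at month 3.

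**The concern.** A patient treated for longer has more time in which to have a first grade 3-4 event or SAE. If entinostat delays progression as the design assumes, arm A accumulates more treatment time. Its proportion with an event then rises even if the risk in each month on drug is the same as on placebo. The planned comparison gives one number per arm for the whole period and nothing with which to interpret a difference.

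This bears on objective 2.2.1, which is to compare the safety profiles. It also matters for timing: under Section 9.2 the data from the first 360 patients would support an FDA submission if PFS is positive, which is when time on treatment is most likely to differ. The plan discusses differential time on treatment for patient-reported outcomes and fixes that comparison at month 3. It makes no such provision for clinician-graded events.

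**Working it through.** **1. The plan's own figure.** I enumerated two Binomial(171) outcomes with rates 24% and 10%, counting those with one-sided Fisher p ≤ 0.025. Power is 92.2%, against the stated 92%. The two-sided 5% test of Section 9.4 also gives 92.2%. With 10% in both arms the one-sided test rejects in 1.6% of trials at 171 per arm and 1.9% at 285 per arm.

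**2. Inputs.**
- From the documents: median PFS 4.1 months on arm B; design hazard ratio 0.58; phase 2 PFS hazard ratio 0.73 (Table 1.1); accrual over 24 months for the first 360 patients and 40 months for all 600; event cut-offs at months 24 and 64; 171 treated patients per arm.
- Assumed: time on treatment equals PFS and is exponential; uniform entry; a constant monthly toxicity hazard h, equal in both arms; 285 treated per arm at the final analysis (300 × 0.95, the same 5% never treated).

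**3. Formula.** With stopping hazard μ and available follow-up f, the proportion with an event on treatment is

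I = average over f of h/(h+μ) × [1 − exp(−(h+μ)f)],

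where f is uniform on 0-24 months (PFS analysis) or 24-64 months (final analysis). For arm B, μ = ln2/4.1 = 0.169. For arm A, μ is 0.58 or 0.73 times that. I solved h for the arm B rate and applied it to arm A.

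**4. Results.** At hazard ratio 0.58, mean time on treatment is 6.3 months (A) against 4.5 (B) at month 24, and 10.0 against 5.9 at month 64. For an arm B rate of 10%, h is 0.0246 and 0.0188 per month respectively.

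| PFS HR | Analysis (n per arm) | Arm B | Arm A | Fisher rejects |
|---|---|---|---|---|
| 0.58 | PFS (171) | 10% | 13.6% | 14% |
| 0.58 | PFS (171) | 20% | 26.4% | 25% |
| 0.58 | Final (285) | 10% | 15.9% | 51% |
| 0.58 | Final (285) | 20% | 30.0% | 76% |
| 0.73 | PFS (171) | 10% to 20% | 12.1% to 23.7% | 6% to 10% |
| 0.73 | Final (285) | 10% to 20% | 13.2% to 25.5% | 18% to 31% |

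**5. How much of the rise from 14% to 51% is sample size.** At 285 per arm, 13.6% against 10% is rejected in 23% of trials. At 171 per arm, 15.9% against 10% is rejected in 31%. Both the wider contrast and the larger sample contribute.

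**6. Early risk only.** If events can occur only in the first 12 weeks, 10% on arm B becomes 10.9% on arm A, and the test rejects in about 3% of trials at 171 per arm.

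**7. What the design contrast means per month.** Without a data cut-off, I/(1−I) = h/μ. The 24% against 10% contrast is then a monthly rate ratio of (0.24/0.76)/(0.10/0.90) × (4.1/7.1) = 2.84 × 0.577 = 1.64, where the ratio of proportions is 2.4.

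**8. Would an exposure-adjusted rate be a safe replacement?** Under constant equal risk without a cut-off, a simulated rate comparison rejects in 2.2% of trials, against 34% for Fisher's test. Now confine risk to the first 12 weeks and give arm A a true 1.5-fold hazard, with hazard ratio 0.58 and arm B at 10%. The crude risk ratio is about 1.59. With total treatment time as denominator, the rate ratio is 1.13 at month 24 and 0.94 at month 64. With time to first event as denominator, it is 1.21 and 1.01. A real excess largely or wholly disappears.

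**The case against.** The strongest reply is that the plan uses a different estimand and makes no error. Patients with an event over all treated patients estimates the risk of the regimen as given, its duration included, and objective 2.2.1 does not ask for a monthly rate. In the scenarios above the cumulative proportions do differ, so a rejection correctly detects a difference in the planned measure. This stands. A reader might infer that Fisher's test is invalid here, or that 14% and 51% are false-positive rates. The documents do not support that: the figures show only how often a significant result would arise with no difference in monthly risk.

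A reader might also infer that no fixed-time or time-to-event look at toxicity exists. That goes too far. Section 9.6 compares fatigue, nausea, anorexia and diarrhea at month 3, and time to treatment deterioration in Section 9.3.3 includes symptom worsening. The gap concerns clinician-graded events. The crude definition and Fisher's test in Section 9.4 apply to deaths and SAEs; for grade 3-4 toxicity the test appears only in the power statement of Section 9.3.2.

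The size also rests on assumptions that the documents do not make. Section 5.4 stops treatment for repeated dose omission through toxicity, which could shorten exposure on arm A and shrink or reverse the effect. Constant monthly risk is not stated anywhere, and Section 9.6 expects month 3 to give the best assessment of treatment-emergent symptoms. Finally, a crude measure that errs toward showing harm is the safer error for an investigational agent. That is a good reason to keep it, but it does not help to interpret a difference once found.

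**Conclusion.** The point holds as a gap in interpretation. As planned, the clinician-graded comparison cannot distinguish higher toxicity risk from longer treatment, in the scenario for which the trial is powered. With equal monthly risk and an arm B rate of 10% to 20%, the test rejects in 14% to 25% of trials at the PFS analysis under the design hazard ratio, and in 6% to 10% under the phase 2 ratio. At the final analysis the ranges are 51% to 76% and 18% to 31%, inflated partly by the larger sample. With risk confined to the first 12 weeks the effect almost vanishes.

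These figures assume that time on treatment follows PFS, that the hazard is constant, and that entinostat prolongs PFS. If it does not, the issue does not arise. Toxicity is a secondary endpoint, so the PFS and OS error rates are unaffected. A reader might conclude that an exposure-adjusted rate ratio should replace the planned test. That does not follow, because such a ratio can hide an early excess on arm A. The supported conclusion is to add to the planned analysis.

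**What to change.** In Sections 9.3.2 and 9.4, keep the crude-incidence Fisher comparison and pre-specify beside it:

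- **Common early window.** Incidence of grade 3 or higher events and of SAEs by arm over, for example, the first 3 cycles, matching the month-3 comparison of patient-reported outcomes.
- **Time to first event on treatment.** A between-arm comparison for the same events, with cumulative incidence curves by arm in which stopping treatment or death is a competing event. The at-risk period should be defined. The cumulative incidence describes what patients experience; the comparison of event hazards while on treatment addresses the question of exposure.
- **Time on treatment by arm**, reported with the toxicity tables.

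Any exposure-adjusted rate ratio should be labelled descriptive. Section 9.4 should also name the test for grade 3-4 toxicity, which now has to be inferred from the power statement.

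The cost is wording and a few tables. Toxicity is assessed and doses are counted every cycle, so timing to the cycle is available without new data collection, and the sample size does not change. The downside is more than one toxicity comparison to interpret, so the plan should say in advance what each is for.

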#### 9.3.3 Time to Treatment Deterioration (TTD)

Another secondary endpoint of the study is to evaluate time to treatment deterioration (TTD) of arm A vs. B. TTD is a composite endpoint and it captures toxicity (measured by symptom worsening), symptom worsening due to disease progression between radiological tumor assessments (provided symptoms are being assessed more frequently than the radiological disease assessments), radiological confirmed disease progression and death. TTD is defined as time

from randomization to radiological confirmed disease progression or death or worsening of symptoms, whichever occurs first. Disease progression is assessed per RECIST v1.1. Symptoms deterioration will be measured by 6 items from the 8-item FACT-Breast Symptom Index (FBSI). The 6 items (GP1, GP2, GP4, GF7, B1, P2, scored 0-24) were selected as being most clinically relative and most responsive to “proximal” change based from clinical deterioration. In addition, the other two items (GP3 or GE6) in the 8-item FBSI will be collected as well for explanatory analysis.

The selected 6 items capture both symptoms related to progressive breast cancer (fatigue, malaise, pain, shortness of breath, overall change in QOL) as well as symptoms related to entinostat (fatigue, nausea, overall change in QOL). According to Yost et al, the minimally important difference (median 2.2, range 1.5-2.5) and anchor-based criteria overlapped (PSR 2.8 and 3.2), and based on these criteria, 2-3 point changes in this 8-item FBSI survey can be interpreted as a MID. To be conservative, symptom deterioration is defined as two consecutive available decreases of at least 3 points from baseline using the 6-item FBSI in this trial, and the second visit time will be used as the time of symptom deterioration in this case, unless it is the final score, for which one decrease is sufficient.

In order to fully capture the impact of toxicity and disease progression before radiological assessment on patient’s QOL, symptoms will be assessed every cycle for the first six months after randomization, every two cycles between 6 months and 1 year. It then will be assessed based on the same schedule for tumor assessments until disease progression. Since symptom change cannot be associated with protocol therapy if the patient never receives any treatment on protocol, the primary population for the TTD analysis will be the enrolled 360 patients for the PFS analysis who receive at least one dose of protocol therapy (i.e., all treated patients in the first 360 enrolled patients). TTD will not be evaluated on the additional 240 patients primarily enrolled for the OS endpoint.

Because we expect that the benefits from improving PFS (and thus less symptoms from disease) on arm A will outweigh any increase in toxicity from the addition of entinostat to exemestane (more symptoms from the treatment), we hypothesize that the combination arm (A) will have a significantly longer TTD than arm B. It is expected that symptom deterioration will occur before radiological confirmed disease progression or death for some patients. Hence, the median TTD should be shorter than the median PFS for the same patient population. To be conservative, we assume that the median TTD is 4 months for patients on arm B, similar with our estimate for PFS in these patients. Assuming 9 patients (9/180=5%) will not start protocol therapy in each arm, with 171 evaluable patients per arm, there is 88% power to detect a HR of 0.67 for arms A/B based on the log-rank test when the analysis is conducted 30 months after study activation (same time as the primary analysis of PFS), assuming a median TTD

of 6 months on arm A (i.e., 50% improvement in median TTD), with a 2.5% one-sided type I error rate.

Rev. Add5

9.4 Analysis Plan for Primary Endpoints, Objective Response, Toxicity and Time to Treatment Deterioration

The primary endpoints are progression-free survival (PFS) and overall survival (OS). Both of the two endpoints will be used for potential entinostat registration with FDA. ORR, toxicity and TTD are secondary endpoints. The primary analysis of PFS will include follow-up through the 247th PFS event within the first 360 patients enrolled. For the primary analysis, progression will be defined by central review. A sensitivity analysis for PFS will be performed using the first 360 patients based on progression defined by local investigators. The TTD analysis will include similar follow-up. The primary analyses of ORR and toxicity will include the first 360 patients enrolled. Final analysis for OS is expected to be conducted at about 70 months after study activation (40 months of accrual + 24 months of follow up + 6 months of data collection and cleaning). At the time of the final OS analysis, secondary analyses of the other endpoints (PFS, ORR and toxicity) including all cases enrolled will be conducted. The secondary analysis of PFS will be conducted in all 600 patients based on progression defined by the local investigators since central review is anticipated for the first 360 patients only.

Tumor response will be assessed per Response Evaluation Criteria In Solid Tumors (RECIST) version 1.1 following the standard ECOG-ACRIN review procedures. PFS is defined to be time from randomization to the earliest documented disease progression as defined by the RECIST criteria, new primary breast cancer, or death without progression. Disease assessment will continue until disease progression, even after non-protocol anti-cancer therapy is started. Cases with incomplete follow up or without adequate disease evaluations will be censored at the date last documented to be free of progression, regardless of whether non-protocol anti-cancer therapy is started or not. As a sensitivity analysis, PFS will also be defined in the following ways: 1) Considering the start of a new non-protocol anti-cancer therapy as a PFS event, in addition to disease progression, new primary breast cancer and death without progression. 2) Censoring PFS observation at the last assessment before a new non-protocol anti-cancer therapy is started for the patients who start new anti-cancer therapy without a documented PFS event. OS is defined to be time from randomization to death from any cause. Cases who are still alive will be censored at the date last known alive. ORR is defined as the proportion of patients with complete response (CR) or partial response (PR) among all patients (including patients with unevaluable tumor response).

All primary analyses regarding PFS, OS and ORR will be based on intention-to-treat population regardless of eligibility status. A secondary analysis for PFS, OS and ORR will be conducted in eligible patients. The distributions of PFS and OS will be estimated using the Kaplan- Meier method (1958), with 95% confidence intervals calculated using Greenwood's formula. In the primary analyses of PFS and OS, differences in treatment effect will be tested using stratified log rank tests, stratifying on the randomization stratification factors. Stratified univariate and multivariable Cox proportional-hazard models (1972) will be built to estimate the hazard ratios (HRs) for treatment effect for PFS and OS as a supportive analysis. In the multivariable Cox models, known prognostic factors will be included as covariates when appropriate, such as age at diagnosis, race/ethnicity, body mass index (BMI), ECOG performance status, disease stage

at diagnosis, prior adjuvant chemotherapy, prior hormonal therapy, et al. The assumption of proportionality in the Cox models will be assessed by investigating the weighted Schoenfeld residuals for each predictor. Patients with missing values for covariates will be excluded from modeling when the proportion of missingness is less than 5% and will be imputed appropriately if the proportion of missingness is  $\geq 5\%$ . ORR will be summarized along with the exact binomial 95% confidence interval and compared between the two arms using Fisher's exact tests.

TTD is defined as time from randomization to disease progression or death or worsening of symptoms, whichever occurs first. All primary analysis for TTD will be based on all cases receiving at least one dose of protocol treatment (i.e., all treated population). The distribution of TTD will be estimated using Kaplan-Meier method, and TTD comparisons between treatment arms will be tested primarily using log-rank test. Cox proportional-hazards models will be conducted to estimate the HR for treatment effect for TTD as a supportive analysis. Same factors included in the multivariable Cox model for PFS and baseline symptom level will be included as predictors for TTD.

Analyses pertaining to toxicity will be based on all treated cases. Adverse events will be graded using the National Cancer Institute (NCI) Common Terminology Criteria for Adverse Events (CTCAE). All treatment-emergent and baseline adverse events and hematological/biochemical toxicities based on laboratory measurements, as well as drug related AE's, will be summarized by treatment group and NCI CTCAE worst grade. The incidence of deaths and treatment-emergent serious adverse events (defined as number of patients experiencing the AE divided by all treated patients) will be summarized and compared between treatment arms using Fisher's exact test. Also, the incidence of adverse events leading to discontinuation of investigational product and/or withdrawal from the study will be summarized and listed.

In all analyses, P-values will be two-sided. A level of 0.2% will be considered statistically significant for stratified log rank test for the primary PFS analysis. For OS comparison, the significance level for stratified log rank test will be 4.8%. For all other tests, a level of 5% will be considered statistically significant.

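### The primary TTD test leaves out the four randomization factors, so it would give up some power if those factors predict TTD

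*Combined protocol and SAP*

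**What the plan says.** Section 9.2 allocates patients by a "permuted block algorithm with a 1:1 randomization ratio to arms A and B". It stratifies on the setting of resistance to the non-steroidal AI, geographic region, visceral disease and prior fulvestrant. Each is binary, so there are 2 × 2 × 2 × 2 = 16 cells.

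For PFS and OS, Section 9.4 says that "differences in treatment effect will be tested using stratified log rank tests, stratifying on the randomization stratification factors". For TTD, the same section says that "TTD comparisons between treatment arms will be tested primarily using log-rank test". The power statement in Section 9.3.3 matches: "there is 88% power to detect a HR of 0.67 for arms A/B based on the log-rank test", with 171 treated patients per arm, medians of 4 and 6 months, and a one-sided error of 2.5%.

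Covariates enter TTD only through supportive Cox models in Section 9.4, which reuse the PFS covariates and add baseline symptom level. The named covariates are age, race/ethnicity, BMI, performance status, stage, prior adjuvant chemotherapy and prior hormonal therapy. Region, visceral disease and AI-resistance setting are not named, and fulvestrant is covered at most under hormonal therapy. The list is given as examples, so it is not closed. The Cox models for PFS and OS are described as stratified; those for TTD are not. No reason is given for the difference.

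**The concern.** TTD includes the progression and death events that make up most of PFS. Section 5.6.3 singles it out as critical among the secondary endpoints, and it is evaluated only in treated patients among the first 360. Leaving out prognostic stratification factors has two effects. Stratified allocation balances the factors, so the arm difference varies less than the unadjusted log-rank variance assumes, and the true type I error falls below nominal. The hazard ratio averaged over a mixed population also lies closer to 1 than the ratio within strata. Both effects reduce power. What is at stake is part of the planned 88%, not a false-positive risk.

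**Working it through.** **Step 1: reproduce the 88%.** Inputs from Section 9.3.3 are 171 per arm, medians of 6 months (A) and 4 months (B), HR 0.67 and one-sided 0.025. Section 9.2.1 gives 24 months of accrual with no added follow-up; the remaining 6 of the 30 months are data cleaning. With exponential times and uniform accrual, P(event) = 1 − (1 − e^(−24λ))/(24λ), where λ = ln 2/median.

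- Arm A: 24λ = 2.773, P = 0.662, events = 113.2.
- Arm B: 24λ = 4.159, P = 0.763, events = 130.5.
- Total: 243.7.

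Schoenfeld power = Φ(√(243.7/4) × |ln 0.67| − 1.960) = Φ(7.805 × 0.4005 − 1.960) = Φ(1.166) = 87.8%. Using HR 2/3 gives 88.6%. Counting all 30 months as clinical follow-up gives 298.8 events and 93.3%, which does not match. The stated 88% is therefore sound as a log-rank calculation that ignores strata.

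**Step 2: let the factors be prognostic.** The documents give no prevalences or factor effects, so these are assumptions. Prevalences are 0.8, 0.9, 0.6 and 0.3, in the order of Section 9.2, and factor HRs are as in the table. Both simulations use 342 patients, permuted blocks within the 16 cells (block size 4 assumed), the arm B median calibrated to 4 months, a 24-month cut-off and a within-stratum treatment HR of 2/3. Simulation 1 has 6,000 trials per scenario; simulation 2 has 3,000 for power. Entries are unadjusted log-rank / 16-stratum log-rank / Cox with four main effects.

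| Factor HRs | One-sided type I error (sim. 1) | Power %, sim. 1 | Power %, sim. 2 |
|---|---|---|---|
| None: 1, 1, 1, 1 | 0.023 / 0.023 / 0.024 | 88.0 / 85.1 / 88.1 | 87.5 / 85.2 / 87.8 |
| Weak: 1.3, 1.1, 1.3, 1.2 | 0.024 / 0.025 / 0.025 | 87.2 / 85.8 / 88.3 | 86.7 / 84.9 / 88.0 |
| Moderate: 1.5, 1.2, 1.5, 1.4 | 0.021 / 0.024 / 0.024 | 85.5 / 85.4 / 87.9 | 85.1 / 85.1 / 87.9 |
| Strong: 2, 1.5, 2, 2 | 0.014 / 0.023 / 0.024 | 77.3 / 85.0 / 86.9 | 79.0 / 84.9 / 87.0 |

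Differences in percentage points, simulation 1 then 2:

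- Cox minus unadjusted: 0.1 and 0.3 (none), 1.1 and 1.3 (weak), 2.4 and 2.8 (moderate), 9.6 and 8.0 (strong).
- 16-stratum minus unadjusted: −2.9 and −2.3, −1.4 and −1.8, −0.1 and 0.0, +7.7 and +5.9.
- 16-stratum minus Cox: between −1.9 and −3.1 throughout.

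The two-sided error of the Cox test in simulation 1 was 0.051 to 0.054. With a simulation standard error of √(0.05 × 0.95/6000) = 0.003, that is consistent with 0.05.

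**Step 3: symptom events.** TTD also counts FBSI worsening, which may not depend on these factors. If 40% of the average hazard is assumed unrelated to them (1,200 trials), the strong-scenario gap shrinks from 78.3 vs 86.1% (7.8 points) to 86.2 vs 88.8% (2.6 points). The moderate gap becomes 87.7 vs 88.7% (1.0 point).

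**Step 4: tied times.** FBSI is collected by cycle (Section 5.6.3) and scans are every 12 weeks (Section 7), so many event times coincide. With times rounded to 4-week visits (600 trials per scenario, standard error about 1.4 points), power for unadjusted / Cox-Efron / Cox-Breslow was:

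- none: 87 / 88 / 84%
- moderate: 84 / 87 / 84%
- strong: 76 / 88 / 83%

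A separate 500-trial run (standard error about 1.6 points) gave 86.2 / 85.4 / 81.6% with no effect and 85.0 / 86.4 / 82.2% with moderate effects. Efron shows no loss beyond simulation error; Breslow loses 3 to 5 points when the factors have no effect.

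**The case against.** The strongest reply is that nothing in the plan is wrong. The unadjusted log-rank is valid, it matches its power statement, and the 88% reproduces. Other secondary comparisons between arms (response, patient-reported scores, adherence) are also unadjusted, so keeping stratified tests for the primary endpoints is a coherent convention. All of that stands.

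The size of the loss also rests on assumed factor effects, and the strong scenario is the least apt for an endpoint that partly counts toxicity-driven symptoms. That stands too, and it is why the loss is given as a range.

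The supportive Cox model answers the point only in part. Its named covariates omit at least three of the four factors, and it would not change the primary p-value.

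A reader might infer more than the documents support:

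- **That the type I error is inflated or the TTD result unreliable.** The error moves the other way.
- **That the 88% was miscalculated.** It was not.
- **That TTD should be tested exactly as PFS is, for consistency.** Stratifying on all 16 cells with about 244 events costs power when the factors are weak and only breaks even at moderate strength.
- **That the trial is known to lose power.** The documents contain nothing on how strongly the factors predict TTD.

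**Conclusion.** The point holds as an efficiency matter on a secondary endpoint. The primary TTD test ignores factors that the design already balances, and it becomes conservative to the extent that they are prognostic. The loss is negligible if they are weak and worth having back if they are moderate. It is substantial only under strong effects that also govern the symptom component. These sizes rest on the assumed prevalences and factor HRs, proportional hazards, and reading the treatment HR as a within-stratum ratio. The direction does not depend on the particular values chosen. Main-effects adjustment showed no measurable loss in any scenario, provided that ties are handled by Efron's or the exact method.

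**What to change.** In Section 9.4, make the primary TTD test the treatment term of a Cox model with the four randomization factors, as recorded at randomization, as main-effect covariates. State the tie method (Efron or exact) and the test statistic; the figures above use Wald. Keep the unadjusted log-rank as a sensitivity analysis. Do not substitute a log-rank stratified on all 16 cells.

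The cost is about one sentence, with no new data. The 88% in Section 9.3.3 can stay if it is labelled as an unadjusted calculation. The change must be made before unblinding and by people who have not seen results by arm, since Section 9.2.1 lets the study statistician and the monitoring committee hold the PFS comparison before release.
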